7.11.3 Vital Signs

For phase 1 descriptive statistics for vital sign results (diastolic and systolic blood pressure, heart rate and body weight) will be summarized as follows:

- Baseline value (C1D1 or screening if C1D1 is not available).
- Minimum post-baseline value.
- Change to Minimum post-baseline value.
- Maximum post-baseline value.
- Change to Maximum post-baseline value.

Changes to the minimum and maximum post-baseline values will be calculated relative to the baseline value.

In addition to the above for phase 2 the actual values and change from baseline will be summarized over time for each cohort up to 6 cycles.

7.11.4 12-Lead ECGs

For phase 1 descriptive statistics for ECG parameters (ventricular rate, PR, QRS, QT, and QTc (Fridericia)) will be summarized as follows:

- Baseline value (C1D1 or screening if C1D1 is not available).
- Minimum post-baseline value.
- Change to Minimum post-baseline value.
- Maximum post-baseline value.
- Change to Maximum post-baseline value.

The number and percent of subjects with increases >30 ms and >60 ms from pre-dose in QTcF will be summarized.

In addition, for phase 2 the actual values and change from baseline will be summarized over time for each cohort up to 6 cycles (including 2H and 4H post-dose values at Cycle 1 Day 1 and Cycle 1 Day 15 visits). The number and percent of patients with increases >30 ms and >60 ms from pre-dose in QTcF will also be summarized over time up to 6 cycles.

All QT values will be converted to QTcF using Fridericia's correction:

$$QT_F = \frac{QT}{\sqrt[3]{RR}(\text{sec})}$$

[Note: RR = 60 seconds/ventricular rate in beats/minute]

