## **MLN0128**

### **Clinical Study Protocol C31001 Amendment 6, EudraCT: 2014-001921-34**

- Baseline prolongation of the rate-corrected QT interval (QTc; eg, repeated demonstration of QTc interval >480 msec, or history of congenital long QT syndrome, or torsades de pointes).

12. Diagnosed or treated for another malignancy within 2 years before administration of the first dose of MLN0128 or previously diagnosed with another malignancy and have any evidence of residual disease. Patients with nonmelanoma skin cancer or carcinoma in situ of any type are not excluded if they have undergone complete resection.

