**ECG Analysis**

ECG intervals (QT and QTc with Fridericia correction, PR, and QRS) and ventricular rate will be summarized at each scheduled time point, along with mean change from Baseline to each posttreatment time point. The number and percentage of patients with ECG abnormalities will be summarized at each time point.

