5.0 ANALYSIS ENDPOINTS

The primary endpoints include:

Phase 1b

- Adverse events, SAEs, assessments of clinical laboratory values, vital sign measurements, physical examination findings, and electrocardiograms (ECGs).

Phase 2

- CBR-16.

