7.13 Changes in the Statistical Analysis Plan

The exemestane concentrations will not be summarized and exemestane PK parameters will not be estimated and/or reported due to the limited amount of PK evaluable data.

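### The SAP drops the protocol's count of patients with ECG abnormalities without declaring it, and its only ECG counts (QTcF rises above 30 and 60 ms) can miss patients who pass 480 ms

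*SAP*

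**What the plan says.** **Protocol 8.1.8, ECG Analysis.** ECG intervals and ventricular rate are to be summarized by time point with mean change from baseline. A patient-level count follows: "The number and percentage of patients with ECG abnormalities will be summarized at each time point". The protocol does not define an abnormality, and it does not restrict the term to QTc.

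**Protocol 5.2.1, exclusion criterion 11.** Baseline QTc prolongation is excluded. One of the examples given is "repeated demonstration of QTc interval >480 msec". No correction formula is named.

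**SAP 7.11.4, phase 1.** Descriptive statistics are planned for the baseline, the minimum, the maximum ("Maximum post-baseline value") and the changes to them. The only count is "The number and percent of subjects with increases >30 ms and >60 ms from pre-dose in QTcF will be summarized".

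**SAP 7.11.4, phase 2.** Actual values and changes over time are added for up to 6 cycles, and the count is repeated: "The number and percent of patients with increases >30 ms and >60 ms from pre-dose in QTcF will also be summarized". Neither phase has a category for PR, QRS or absolute QTcF.

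**SAP 7.13.** The single declared change concerns exemestane pharmacokinetics: "The exemestane concentrations will not be summarized and exemestane PK parameters will not be estimated and/or reported".

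**SAP 9.0.** None of the readable entries in the list of subject-level listings is for ECGs. Two entries are redacted.

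ECGs are one component of the phase 1b primary safety endpoint and of a secondary endpoint (Protocol 3.1 and 3.2; SAP 5.0 and 5.1).

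**The concern.** The protocol promises a count of patients. The SAP supplies two change categories in its place and does not say that anything was dropped.

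A change category and an absolute category answer different questions. A rise of more than 30 or 60 ms shows how far a patient moved. It does not show where she ended. The gap is widest for patients who start high, and eligibility allows a QTc up to 480 ms. The only ECG outlier table could therefore show no patients in either category although some have passed the level that the protocol uses as its own example of prolongation. A reader of the study report would have no count to show it. PR and QRS abnormalities, which the protocol's wording also covers, have no count at all.

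**Working it through.** The plan gives no figure to reproduce here. The check has two parts.

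**1. Protocol against SAP.**

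| Item | Protocol 8.1.8 | SAP |
|---|---|---|
| Patients with an ECG abnormality, by time point | Planned | Absent from 7.11.4 |
| QTcF rise above 30 and 60 ms | Not mentioned | Planned, both phases |
| Absolute QTcF category | Not specified | Absent |
| Declaration of the difference | – | Absent from 7.13 |

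**2. Which eligible patients the change categories miss.** Inputs:

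- Highest baseline allowed by the example in exclusion criterion 11: 480 ms.
- Change cut-offs in SAP 7.11.4: above 30 ms and above 60 ms.
- Assumptions: values are whole milliseconds, and the 480 ms level is applied to QTcF.

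Let b be the baseline and r the largest rise. A patient passes a level L when b + r > L. She enters neither category when r ≤ 30. Both can hold when b > L − 30, with b ≤ 480.

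- For L = 480: b > 480 − 30 = 450, so b runs from 451 to 480 ms. At b = 480 the smallest sufficient rise is 481 − 480 = 1 ms.
- With r ≤ 60: b > 480 − 60 = 420. From 421 to 450 ms a patient can pass 480 ms on a rise of 31 to 60 ms. She is then in the >30 ms row, but nothing shows that 480 ms was passed.

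The same arithmetic for 500 ms, a level that does not come from the documents and is used only as an illustration:

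- b > 500 − 30 = 470, so b runs from 471 to 480 ms. A baseline of 470 does not qualify, because 470 + 30 = 500 does not exceed 500.
- At b = 480 the smallest sufficient rise is 501 − 480 = 21 ms.
- With r ≤ 60: b > 500 − 60 = 440, so b runs from 441 to 480 ms.

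Example: a patient at 475 ms who reaches 503 ms has risen by 503 − 475 = 28 ms. She has passed 480 ms and is in neither category.

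**How much it could matter.** The documents do not give the baseline QTc distribution, so the number missed could be zero. Each phase 1b treatment cohort has 6 patients, so one missed patient would be 1/6 = 16.7% of a cohort, or 1/24 = 4.2% of phase 1b.

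**The case against.** The case against has several good points.

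- **The patient is not invisible.** A value of 503 ms would appear as the maximum in the descriptive statistics. Protocol 9.2 treats a clinically relevant deterioration in a clinical finding as an adverse event, and SAP 7.11.1 tabulates treatment-emergent events by preferred term. In phase 1b, related nonhematologic toxicity of Grade 3 or higher is a DLT, with two stated exceptions (Protocol 6.2), and Cycle 1 DLTs are listed. This stands: a reader might infer that such a patient leaves no trace, and the documents do not support that. But a maximum shows one value and not how many patients passed a level. The adverse event route depends on investigator reporting, and QT prolongation is not among the SAP's adverse events of interest.
- **The 480 msec figure is only an entry example.** It describes repeated baseline findings. It is not an on-treatment limit, and the protocol does not promise absolute QTcF categories. This stands. The figure is used here because it is the one QTc level that the protocol gives, and because the promised count needs some definition.
- **A 500 ms category has no source in the documents.** This stands, so it can only be the sponsor's option.
- **Rises measured from pre-dose might be read as same-day changes.** On that reading, prolongation already present before the day's dose would drop out. The SAP largely answers this. Section 7.1 treats Cycle 1 Day 1 values as pre-dose, and 7.11.4 names Cycle 1 Day 1 as the baseline, with screening as fallback. What remains is a point of wording.
- **No decision rule uses these counts.** This is true, and it limits the weight of the point. It does not remove the undeclared departure.

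**Conclusion.** The concern holds as an undeclared gap between protocol and SAP with a definite blind spot. The count of patients with ECG abnormalities is missing from SAP 7.11.4, and 7.13 does not say so. Eligible patients with a baseline of 451 to 480 ms can pass 480 ms and enter neither planned ECG category.

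This rests on whole-millisecond values and on applying the 480 ms example to QTcF. The absence of an ECG listing is supporting evidence only, because two entries in 9.0 are redacted.

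The documents do not show that any patient will be missed, that safety conclusions will change, or that the protocol set 480 or 500 ms as a limit on treatment. The correction is worth making because ECGs are an endpoint component and the data are already collected. No efficacy result or dose decision is shown to depend on it.

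**What to change.** 1. **SAP 7.11.4, both phases.** Restore the protocol's count and percentage of patients with an ECG abnormality at each time point, and define what qualifies. Include post-baseline QTcF above 480 ms, by time point and for the worst post-baseline value, among patients not above that level at baseline. A higher absolute category, such as above 500 ms, may be added as the sponsor's choice.
2. **SAP 9.0.** Add a by-subject listing of the patients counted.
3. **SAP 7.13.** Declare any part of the protocol's ECG-abnormality count that will not be produced.
4. **Wording only.** In the >30 and >60 ms rule, replace the pre-dose reference with baseline, stated as the Cycle 1 Day 1 pre-dose reading with the screening value as fallback, in line with 7.1.

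The cost is SAP text, a few table rows and one listing. No new ECGs or procedures are needed.

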7.11.5 Other Observations Related to Safety

Not Applicable

7.12 Interim Analysis

There will be 3 interim analyses for futility in the Everolimus-Resistant Cohort and 2 interim analyses for futility in the Everolimus-Sensitive Cohort. The investigator-assessed CBR-16 rate will be used as the endpoint for the interim analysis. The interim analysis will be based on response-evaluable patients who have had the opportunity to complete a minimum of 4 cycles of treatment with MLN0128 or have discontinued treatment with MLN0128 before the end of Cycle 4.

In the Everolimus-Resistant Cohort, there will be 3 interim analyses based on the following assumptions:

- Ineffective CBR-16 rate (Ho): 10%.

- Effective CBR-16 rate (Ha): 20%.
- Alpha = 10%; power = 80%.
- Prior Beta Distribution Parameters: $a_0 = 0.10$, $b_0 = 0.90$.
- Probability of early termination under H_0 : 68%.

Timing of Interim Analyses in the Everolimus-Resistant Cohort

Stage	No. of Patients Evaluated	Number of Patients With CBR-16 to Proceed or Declare Active
1	29	≥ 3
2	39	≥ 4
3	49	≥ 6
Final	56	≥ 9

Abbreviations: CBR-16 = defined as the proportion of patients who achieve complete response or partial response of any duration, or stable disease) ≥ 16 weeks; No. = number.

In the Everolimus-Sensitive Cohort, there will be 2 interim analyses based on the following assumptions:

- Ineffective CBR-16 rate (H_0): 15%.
- Effective CBR-16 rate (Ha): 30%.
- Alpha = 5%; power = 80%.
- Prior Beta Distribution Parameters: $a_0 = 0.15$, $b_0 = 0.85$.
- Probability of early termination under H_0 : 71%.

Timing of Interim Analyses in the Everolimus-Sensitive Cohort

Stage	No. of Patients Evaluated	Number of Patients With CBR-16 to Proceed or Declare Active
1	23	≥ 4
2	38	≥ 7
Final	48	≥ 12

Abbreviations: CBR-16 = defined as the proportion of patients who achieve complete response or partial response of any duration, or stable disease) ≥ 16 weeks; No. = number.

7.13 Changes in the Statistical Analysis Plan

The exemestane concentrations will not be summarized and exemestane PK parameters will not be estimated and/or reported due to the limited amount of PK evaluable data.

9.0 DATA LISTINGS

The below subject-level listings will be generated:

- Disposition (date of first dose, date of last dose, number of cycles, reason for discontinuation of study treatment).
- Populations (can be included with disposition listing).
- Demographics.
- Baseline characteristics.
- Prior therapy.
- Study drug exposure.
- TEAEs leading to study drug discontinuation.
- TEAEs resulting in dose modifications.
- Serious AEs.
- On-study deaths.
- DLTs during Cycle 1 (Phase 1b).
- Pharmacokinetic concentrations (including sampling times) for MLN0128 and Exemestane.
- Pharmacokinetic parameters for MLN0128.
- CCI [REDACTED]
- CCI [REDACTED]
- Efficacy (target lesions, non-target lesions, investigator assessment of response, best response (confirmed and unconfirmed), duration of response, duration of stable disease).

ELECTRONIC SIGNATURES

Signed by	Meaning of Signature	Server Date (dd-MMM-yyyy HH:mm 'UTC')
PPD 	Biostatistics Approval	25-Jul-2018 19:29 UTC
	Clinical Science Approval	25-Jul-2018 19:46 UTC
	Clinical Pharmacology Approval	26-Jul-2018 01:09 UTC
	Biostatistics Approval	26-Jul-2018 14:21 UTC
